otherwise eligible for the study will be allowed to participate in the study but will not be randomized to the intervention for which they have a contraindication. In Sections 10.1 (Acceptance Commitment Therapy), 10.2 (Duloxetine), 10.3 (Enhanced Self Care), and 10.4 (Evidence-Based Exercise and Manual Therapy) specific details regarding risk assessment and mitigation are given for each study intervention.

Participants will be advised that they should contact study staff regarding any side effects or unexpected adverse events that occur while enrolled in the study. Prior to the start of a new study intervention, participants will be informed that if they are unable to tolerate the intervention, they are permitted to cease the intervention. Specifically for duloxetine, participants will be instructed on how to safely taper off the medication. In addition, study staff will conduct a phone call assessment with all participants approximately midway into each of the two intervention periods to evaluate pain-related outcomes as well as to ascertain how well the participant is tolerating their current study intervention(s). Participants who indicate they are unable to tolerate the intervention will be safely transitioned off their current intervention but, if in intervention period one, will be allowed to be randomized to a new intervention in the second study period. Additionally, all participants will be assessed for unexpected and adverse events 4 weeks after the end of the second intervention period (i.e., after completion of all study treatment).

Acceptance Commitment Therapy: Participants will interact with their therapist at least weekly, and the therapist will provide support as well as monitor for worsening of depression or anxiety symptoms including suicidal ideation. Participants will be encouraged to contact study staff with questions or concerns throughout the course of the study.

Duloxetine: Participants on duloxetine will be monitored appropriately for clinical worsening, suicidality, or unusual changes in behavior. Participants may be referred for appropriate treatment including emergency services if required. Participation can also be discontinued if there is active suicidal ideation.

Enhanced Self Care: The ESC intervention is an educational and self-care digital intervention. Risks are minimal; therefore, no intervention-specific risk mitigation is planned.

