8. STUDY POPULATION

8.1. STUDY INCLUSION CRITERIA

To be eligible, an individual must meet all of the following inclusion criteria:

- Ability to read and understand English
- Provision of signed and dated informed consent form(s)
- Willing and able to receive study-related messages and survey links via email
- Willing and able to receive study-related phone calls
- Age 18 years old or older
- Low-back pain for at least 3 months and occurring on at least half the days in the past 6 months
- Contraindicated to no more than one of the study interventions at the time of eligibility assessment(s)
- Eligible to receive at least three of the four study interventions and willing to receive any intervention for which they are eligible
- A PEG score 4 or higher prior to the Run-in period
- Willing and able to undergo required phenotyping as defined in Section 9
- Regular reliable access to an internet-enabled device such as a smart phone, tablet, or laptop computer
- Meet Run-in period engagement eligibility criteria:
 - Completion of two Run-in study information modules prior to period 1 randomization (Visit 0)
- Low-back pain more severe than pain in other parts of the body
- Available to complete the full study protocol (approximately 9 months)

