8.3. STUDY INTERVENTION CONTRAINDICATIONS

ACT intervention contraindications

An individual who meets any of the following criteria will be excluded from being randomized to receive ACT during the study:

Currently receiving or intending to receive within the next few months any pain-specific
psychotherapy, e.g., Cognitive Behavioral Therapy, directed towards pain even if it is only a part
of the treatment, and delivered by a psychologist or social worker

Duloxetine intervention contraindications

An individual who meets any of the following criteria will be excluded from being randomized to receive duloxetine during the study:

- Pregnant: If the participant becomes pregnant during the study, duloxetine will be rapidly tapered.
- Currently taking any of the following:

Duloxetine

Lithium

Tramadol (Ultram, Ultracet)

St. John's Wort

Prochlorperazine (Compazine)

Thioridazine (a psychiatric medication)

Propafenone or Flecainide (for heart rhythm problems)

Ciprofloxacin (Cipro, an antibiotic)

Linezolid (Zyvox, an antibiotic)

Methylene Blue

Cimetidine (Tagamet, for heartburn)

Bupropion (Wellbutrin)

SNRIs:

Venlafaxine

Milnacipran

Duloxetine

Sibutramine

Atomoxetine

Desvenlafaxine

Levomilnacipran

SSRIs:

Sertraline

Paroxetine

fluoxetine

escitalopram

citalopram

fluvoxamine

Vortioxetine (Trintellix)

Any other contraindicated SNRIs, SSRIs, and antidepressants

Reporting a current or previous diagnosis of any of the following

Renal dysfunction

End-Stage Renal Failure

Hepatic dysfunction

- Previous allergic or other severe adverse reaction to duloxetine or, as determined by the site PI, a medicine with duloxetine cross-reactivity.
- History of bipolar disorder, manic episodes, or suicide attempts
- Currently breastfeeding

EBEM intervention contraindications

An individual who meets any of the following criteria will be excluded from being randomized to receive EBEM during the study:

- Currently receiving or intending to receive within the next few months any type of manual therapy or exercise treatment for low-back pain from a licensed provider
- Uncontrolled high blood pressure (≥150 systolic and/or ≥100 diastolic)
- Uncontrolled coronary artery disease
- Inability to walk at least 50 feet unassisted
- Contraindication for manual therapy
- Contraindication for participation in an exercise program

ESC intervention contraindications

An individual who becomes pregnant during the study will be counseled to stop NSAIDs.

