10.4.4. MEASURES TO MINIMIZE BIAS: RANDOMIZATION AND BLINDING

The **first-stage randomization** will use a randomized version⁶¹ of the Minimization method^{62,63} to maintain marginal covariate balance. Minimization is an alternative to stratified permuted block randomization for maintaining (marginal) covariate balance across treatments that is better equipped to handle a larger number of factors to balance on. When a participant is randomized, a measure of the marginal discrepancy between treatments is calculated and the patient is randomized using a biased coin method where whichever treatment would make the discrepancy smallest has a higher probability and the other treatments have equal, smaller probabilities. Covariates included in minimization algorithm:

[figure not shown]
- Willingness to participate in deep phenotyping (yes/no)
- Depressive or anxiety symptoms (yes/no)
- Duration of pain symptoms (<5 years/≥5 years)
- Current use of opioid treatment (yes/no)

A total of approximately 740 participants will be randomized to ACT (n=185), duloxetine (n=185), ESC (n=185), and EBEM (n=185) and which will require recruitment of approximately 820 participants, anticipating that 10% will not be randomized due to failure to meet eligibility criteria at the end of the run-in phase and an estimated 15% will be lost to follow-up over the course of the study. Participants who did not complete required run-in procedures will not be randomized. In order to assign equal numbers of participants to each of the 4 study interventions, randomization probabilities will account

for the fact that certain participants, e.g., because of a contraindication, may be eligible for only 3 of the 4 treatments.

Second-stage randomization will occur at the end of the first treatment period. Response to treatment will be assessed using the PEG and PGIC. Based on these scores, individuals will be grouped into 4 response classes.

- Group 1 participants (PGIC 1-2 and PEG <4) are assigned to maintain the first-line treatment.
- Group 2 participants (PGIC 1-2, PEG ≥4) are assigned to maintain the current treatment and augment with a randomly selected additional treatment.
- Group 3 participants (PGIC 3-4) are randomized to an **augmentation treatment or to switch** to a new treatment.
- Group 4 participants (PGIC 5-7) are randomly assigned to switch to a second-line treatment.

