#### Trial/Study Design

Study data for this analysis will be from the BEST Trial, which has been described elsewhere. The trial follows a two stage sequential multiple assignment random trial SMART trial plan. The trial is split into two 12-week intervention stages with 3 study visits that occurred at the beginning of Stage 1 (Visit 0/Week 0), Stage 2 (Visit 1/Week 12), and the end of Stage 2(Visit 2/Week 24). At baseline (Visit 0/Week 0) participants were randomized to one of four interventions. To participate in the study participants were required to be eligible for a minimum of 3 of the treatments at baseline. A re-randomization happened at Week 12, where participants were assigned to one of four responder status categories using a combination of Week 12 Pain, Enjoyment of Life, and General Activity (PEG) and Patient Global Impression of Change (PGIC) scores. Participants with Week 12 PGIC 1-2 and PEG <= 4 maintained their initial treatment, participant with Week 12 PGIC 1-2 and PEG > 4 were randomized to augment a second treatment, participants with a Week 12 PGIC 3-4 were randomized to either augment a second treatment or switch treatments, and participants with a Week 12 PGIC of 5-7 or participants who could not tolerate their initial treatment were switched to a new treatment. Randomization at the baseline visit was stratified by years of cLBP, depression/anxiety, consent to optional phenotyping, and current use of opioids. The details of the trial are illustrated in the schema below.

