#### Multiplicity Adjustments

We will not use a multiplicity adjustment to adjust for the width of the confidence interval because the least squares mean is not a primary estimand of interest in the trial's statistical design. The primary estimand of interest is the value of the estimated optimal dynamic treatment regime, which is outside the scope of the outcome analysis presented here.

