## **Analysis**

#### **Analysis Methods**

A linear mixed-effect model (LMM) was used to model the least squares mean of the primary and secondary outcomes at Visit 2 (Week 24) by the Stage 1 treatment assignment for all continuous outcomes. Random intercepts and a linear random slope for time were included to account for subject-level variability. The randomization and minimization algorithm variables are included as

fixed effects. Week indicators as fixed effects were included to model non-linear effects of time. An additional fixed effect was included for the number of treatments a participant was eligible for at the baseline visit. Estimation was conducted using REML and modern optimization approaches with the lme4 package in R. Least squares means were estimated for each Week 24 outcome, along with associated 95% confidence intervals, using the emmeans package in R. Due to the small number of participants on opioids in the BEST Trial sample, we only report counts of participants self-reporting opioid use at Week 24.

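### The SAP model adjusts for how many treatments a participant could receive, not which one was barred, so the Stage 1 least squares means may stay confounded by type of contraindication

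*SAP*

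**What the plan says.** The SAP (Analysis Methods) fits a linear mixed model to each continuous outcome and reports Week 24 least squares means by Stage 1 arm with 95% intervals. Besides the randomization and minimization variables and week indicators, eligibility enters once: "An additional fixed effect was included for the number of treatments a participant was eligible for at the baseline visit".

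The entry rule in the SAP (Trial/Study Design) is: "To participate in the study participants were required to be eligible for a minimum of 3 of the treatments at baseline". The same section lists the baseline balancing factors: "Randomization at the baseline visit was stratified by years of cLBP, depression/anxiety, consent to optional phenotyping, and current use of opioids".

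Under protocol Section 5.2.3, otherwise eligible people with a contraindication to one intervention "will be allowed to participate in the study but will not be randomized to the intervention for which they have a contraindication". Section 8.3 sets the bars by treatment. Anyone meeting its duloxetine list, for example, "will be excluded from being randomized to receive duloxetine during the study". Section 10.4.4 says the randomization probabilities account "for the fact that certain participants, e.g., because of a contraindication, may be eligible for only 3 of the 4 treatments", so that arm sizes come out equal.

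**The concern.** Arms are comparable by design only among participants with the same set of permitted treatments. The count does not identify that set. Its 3-eligible level mixes three groups that Section 8.3 defines by different things:

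- **Duloxetine:** current antidepressant or tramadol use; bipolar, manic or suicide-attempt history; renal or hepatic dysfunction; breastfeeding.
- **EBEM:** uncontrolled blood pressure or coronary disease, limited walking, concurrent manual or exercise therapy.
- **ACT:** current or intended pain-specific psychotherapy.

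No baseline condition bars randomization to ESC. The ESC arm can therefore hold all three groups, while each other arm lacks its own. If the groups differ in prognosis, part of any gap between arm means reflects who could be assigned there. The balancing factors do not record which treatment was barred. Depression/anxiety and opioid use are at best partial proxies for the antidepressant and tramadol bars.

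These means are the SAP's only model-based efficacy output, and readers are likely to compare them across arms.

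**Working it through.** **Inputs from the documents.** Arm sizes are ACT 203, duloxetine 198, EBEM 199 and ESC 205, which sum to 805 (SAP baseline table). The count is 3 or 4, and a barred arm has assignment probability zero. The documents attach no figure to this adjustment, so there is none to reproduce.

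**Assumptions.** Shares barred: duloxetine 15–30%, EBEM 8–15%, ACT 4–10%. Base case: 20%, 10%, 5%. There is no true treatment effect. Duloxetine-barred participants score δ = 0.5 PEG points worse (upper value 1.0), and the other groups do not differ. Cell sizes were fitted by iterative proportional fitting to the assumed shares and the actual arm sizes.

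**Base-case cells.**

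| | ACT | Duloxetine | EBEM | ESC |
|---|---|---|---|---|
| Eligible for all four | 123.9 | 151.7 | 129.7 | 117.9 |
| ACT barred | 0 | 15.3 | 13.1 | 11.9 |
| Duloxetine barred | 53.7 | 0 | 56.2 | 51.1 |
| EBEM barred | 25.4 | 31.0 | 0 | 24.1 |
| 3-eligible, m | 79.1 | 46.3 | 69.3 | 87.1 |
| r = m/n | 0.389 | 0.234 | 0.348 | 0.425 |
| q = duloxetine-barred share of m | 0.679 | 0 | 0.811 | 0.587 |
| v = m(n − m)/n | 48.3 | 35.5 | 45.2 | 50.1 |

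**Count-adjusted estimate.** In a linear model with arm and count, the count coefficient is γ = δ·Σvq/Σv = 0.5 × 98.8/179.0 = 0.276. Each arm's spurious coefficient is r(δq − γ):

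- Duloxetine: 0.234 × (0 − 0.276) = −0.065
- ESC: 0.425 × (0.294 − 0.276) = 0.007
- EBEM: 0.348 × (0.406 − 0.276) = 0.045
- ACT: 0.389 × (0.340 − 0.276) = 0.025

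Subtracting duloxetine's coefficient (unrounded) gives bias in its favour of 0.072 vs ESC, 0.110 vs EBEM and 0.089 vs ACT. With no eligibility term these are 0.125, 0.141 and 0.132. With a four-level eligibility-set factor all are 0 under additivity.

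**Over the assumed grid (PEG points; positive favours duloxetine).**

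| Scenario, δ 0.5–1.0 | vs ESC | vs EBEM |
|---|---|---|
| Only duloxetine-barred worse | 0.05 to 0.25 | 0.08 to 0.36 |
| EBEM- and ACT-barred worse by half as much | 0.03 to 0.13 | 0.04 to 0.18 |
| Only EBEM-barred worse | −0.03 to −0.18 | −0.07 to −0.32 |
| Row 1, depression/anxiety in model (80% vs 30%) | 0.05 to 0.22 | 0.08 to 0.31 |
| Row 1, depression/anxiety in model (90% vs 20%) | 0.04 to 0.18 | 0.07 to 0.26 |

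The bracketed percentages are assumed prevalences in duloxetine-barred participants and in everyone else. At δ = 0.5 the row 1 maxima are 0.13 and 0.18. If each barred group is split equally over its three open arms, row 1 becomes 0.05–0.20 and 0.08–0.30.

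**Against precision.** The simple standard error of duloxetine vs ESC is √(1/198 + 1/205) = 0.0996 SD. If the PEG SD is 1.5–2.5 (assumed), that is 0.15–0.25 points. The base-case 0.072 is then 0.3–0.5 standard errors, and a nominal 95% interval for the contrast covers about 92–94%.

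**Against the planned effects.** Protocol Section 13.2 assumes 0.25 SD for ACT, 0.3 for duloxetine and 0.4 for exercise and manual therapy. With the same assumed SD, the base-case bias is 0.110/2.5 to 0.110/1.5 = 0.04–0.07 SD vs EBEM (planned gap 0.10) and 0.089/2.5 to 0.089/1.5 = 0.04–0.06 SD vs ACT (planned gap 0.05).

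**The case against.** The strongest reply is about size and purpose.

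- The top of the range needs 30 + 15 + 10 = 55% of participants barred from something and a full 1.0-point prognostic gap. With 20% barred from duloxetine, 3% from EBEM, 2% from ACT and 0.5 points, the bias is only 0.037 vs ESC and 0.051 vs EBEM.
- The count already removes 24–53% of the unadjusted bias vs ESC over the grid.
- If change from baseline is what is modelled, stable differences in severity cancel and only differential change matters. The SAP outcome table describes PEG both as the Visit 2 score and relative to baseline.
- The SAP plans no hypothesis tests and specifies no between-arm contrast. It also says "the least squares mean is not a primary estimand of interest".
- The by-arm baseline table will show correlates of several bars, such as PHQ-2, GAD-2, blood pressure and gait.

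All of this stands as a limit on size and weight. None of it makes the count sufficient. The correlates in the table do not show which treatment was barred or who takes antidepressants, and an imbalance that is only tabulated stays in the estimates. A descriptive analysis still puts four arm means with intervals in front of the reader.

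The SAP's reference to randomization variables could be read as already covering the eligibility set. However, the SAP then adds eligibility as a separate term, and only as a number.

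**Conclusion.** The concern holds. Under the documents' own allocation rules, the count does not make the arms exchangeable, and the eligibility set does. Whether the reported means are materially affected cannot be settled from the documents: it depends on the shares barred and on whether prognosis differs by barred type beyond the covariates already in the model.

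Under the stated base case the distortion is about 0.07–0.11 PEG points in the duloxetine comparisons. That is below one standard error but similar to some planned gaps between active arms. The direction depends on which barred group does worse. The bias vanishes if barred groups share a prognosis, if only one treatment is ever barred, or if the difference runs wholly through modelled covariates. The point concerns the SAP's outcome report and leaves the dynamic treatment regime objective untouched. It is a worthwhile correction, not a fatal flaw.

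**What to change.** 1. Replace the count with a four-level factor: eligible for all four, not ACT, not duloxetine, not EBEM. Average the least squares means over its observed distribution and state those weights.
2. Tabulate barred type by Stage 1 arm, so readers can judge materiality.
3. Add a sensitivity analysis restricted to participants eligible for all four treatments. The factor relies on additivity, because nobody is ever observed in a barred arm. If duloxetine's effect in duloxetine-barred participants differed by 0.5 points, its mean would shift by 0.5 × 0.15 to 0.5 × 0.30, or about 0.08–0.15 points.

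**Cost.** Two further degrees of freedom and a refit of models that the SAP describes in the past tense. Under the assumed shares, the standard error of the duloxetine contrast rises 1–3% vs ESC and 3–7% vs EBEM. The restricted analysis would keep about 362–588 of the 805, with standard errors 13–47% larger, so it should support the main analysis and not replace it. No new data should be needed: the barred treatment had to be known before randomization, and the SAP (Missing Data) says model covariates were required at that point.

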#### **Outcome Definitions**

Outcome	Outcome Type	Specification	Specific	Calculation to	Analysis
Name	(primary/secondary)	of outcome	measurement	derive	Method
		and timing	and units	outcome	
Patient-	Primary	PEG Score	The PEG scale	Calculate the	LMM
Reported		measured at	is based on a	PEG Score by	
Pain		the Visit 2	participant	averaging the	
Intensity		(Week 24)	rating of their	responses	
and			pain in 3	from each of	
Interference			areas: pain	the 3 scales.	
Score			intensity, pain		
			interference		
			with		
			enjoyment of		
			life, and pain		
			interference		
			with general		
			activities. A		
			rating is given		
			ranging from -		
			10 (lowest) to		
			10 (highest)		
			on each of		
			these scales.		
			We use the		
			average of		
			these ratings,		
			with higher scores		
			indicating		
			increased		
			pain intensity		
			and		
			interference		
			at 24 Weeks		
			compared to		
			Baseline.		
Pain	Secondary	Pain	Ratings of the	Calculate the	LMM
Interference		Interference	consequences	raw score by	

		at Visit 2 (Week 24)	of pain on relevant aspects of one's life. This includes the extent to which the pain hinders engagement with social, cognitive, emotional, physical, and recreational activities. Results range from -34 to 34 (t-scores range from 41.6 to 75.6), with higher scores indicating increased pain interference at 24 Weeks compared to	summing all appropriate responses, then translate the raw score to the corresponding T-Score	
Physical Function	Secondary	Physical Function at Visit 2 (Week 24)	Baseline.  Measured by the PROMIS-PF Short Form 6b. The PROMIS-PF Short Form 6b is a series of 6 questions.  Results range from -37.1 to 37.1 (t-scores range from 21.6 to 58.7), with higher scores indicating increased physical functioning at 24 Weeks	Calculate the raw score by summing all appropriate responses, then translate the raw score to the corresponding T-Score	LMM

			compared to Baseline.		
Depression Score	Secondary	Depression at Visit 2 (Week 24)	Measured by the PROMIS 4-item depression scale from the PROMIS 29 profile. The PROMIS 4-item depression scale from the PROMIS 29 profile is a series of 4 questions. A rating of negative mood, views of self, as well as decreased positive affect and engagement. Results range from -38.4 to 38.4 (t-scores range from 41.0 to 79.4), with higher scores indicating increased depression at 24 Weeks compared to Baseline.	Calculate the raw score by summing all appropriate responses, then translate the raw score to the corresponding T-Score	LMM
Anxiety Score	Secondary	Anxiety at Visit 2 (Week 24)	Measured by the PROMIS Emotional Distress-Anxiety scale (PROMIS-EDA 4a). The PROMIS-EDA 4a is a series of 4 questions. A rating of fear, anxious	Calculate the raw score by summing all appropriate responses, then translate the raw score to the corresponding T-Score	LMM

	T	T	1 .	Τ	 
			misery,		
			hyperarousal,		
			and somatic		
			symptoms		
			related to		
			arousal.		
			Results range		
			from -41.3 to		
			41.3 (t-scores		
			range from		
			40.3 to 81.6),		
			with higher		
			scores		
			indicating		
			increased		
			anxiety at 24		
			Weeks		
			compared to		
			Baseline.		
Sleep	Secondary	Sleep	Measured by	Calculate the	LMM
Disturbance		Disturbance	the PROMIS	raw score by	
		at Visit 2	short form 6a.	summing all	
		(week 24)	The PROMIS	appropriate	
			short form 6a	responses,	
			is a series of 6	then translate	
			questions. A	the raw score	
			rating of sleep	to the	
			quality, sleep	corresponding	
			depth, and	T-Score	
			restoration	1 55515	
			associated		
			with sleep.		
			Results range		
			from -44.4 to		
			44.4 (t-scores		
			range from		
			31.7 to 76.1),		
			with higher		
			scores		
			indicating		
			increased		
			sleep		
			disturbance at		
			24 Weeks		
			compared to		
			Baseline.		
Sleep	Secondary	Response to	Response to		LMM
Duration		BACPAC	"During the		
		sleep	past month,		
		disturbance	how many		
	1	aistai balltt	110 w many	I	

		question at Visit 2 (Week 24)	hours and minutes of actual sleep did you get at night?" measured in Hours and Minutes. Results range from -24 to 24 hours, with higher number of hours indicating increased sleep duration at 24 Weeks compared to Baseline.	
Opioid Incidence	Secondary	Opioid incidence reported at Visit 2 (Week 24)	Self-reported Yes/No/Not Sure response to a single question, "Are you currently taking any opioid pain medication on a daily basis?"	Counts

